4.3 EXCLUSION CRITERIA

Subjects with any of the following criteria will not be accepted into the study:

- Subject is unable to follow consent
- Patient on maximum urate lowering therapy where therapy cannot be escalated further
- Severe renal failure (eGFR <30) or established liver disease

- Current prescription of medication known to interact with xanthine oxidase inhibitors such as azathioprine or mercapto-purine.

For the gut microbiota part of this study - subjects are excluded from the control group if any of the previous or following are present:

- Have a history of gout
- Taking urate lowering therapy
- Have a history of inflammatory bowel disease or colorectal cancer
- Have had oral antibiotics in the previous 3 months
- Have had a total colectomy previously
- Have suffered an infective gastro-intestinal illness in the previous 6 weeks.
- No face to face visits or samples will be arranged for participants that have ever tested positive for, or had symptoms suggestive of, COVID-19

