4.2 INCLUSION CRITERIA

Subjects must meet all of the following inclusion criteria to enter the study:

- Evidence of a personally signed and dated informed consent document indicating that the subject has been informed of all aspects of the study.
- Adult male or female aged ≥ 18 years.
- Confirmed clinical diagnosis of gout as per ACR/EULAR criteria (Neogi T, 2015).
- Physician recommendation that initiation or escalation of urate lowering therapy (Allopurinol or Febuxostat) is required guided by further monitoring of serum urate levels.
- No previous adverse reaction to Allopurinol or Febuxostat.
- Serum urate >0.36 mm/L.
- Patient has a smart phone and is able to use application.

For the gut microbiota part of this study control participants must be:

- Adult male or female aged ≥ 18 years.
- Evidence of a personally signed and dated informed consent document indicating that the subject (or a legally acceptable representative) has been informed of all aspects of the study.

For the extension study

- Patient has completed week 52 of original study
- Evidence of a personally signed and dated informed consent document indicating that the subject has been informed of all aspects of the extension study.

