5 PARTICIPANT SELECTION AND ENROLMENT

5.1 IDENTIFYING PARTICIPANTS

Participants will be identified by the principal investigator or the sub-investigator following assessment by the NHS Lothian Rheumatology service. It is anticipated that most participants will be identified following routine and acute-care referrals to NHS Lothian Rheumatology services by the participants' general practitioner or secondary care physicians, however any appropriate referral will be considered including referrals from out with NHS Lothian. Additional participants will be sought through SHARE - The Scottish Health Research Register which is a register of adults and children aged 11 and over who are willing to be invited to take part in medical research.

Posters raising awareness of the study will be placed in the rheumatology outpatient department, and in Acute receiving units at Western General Hospital and Royal Infirmary of Edinburgh. An email will be sent to General Practitioners in NHS Lothian inviting referral of suitable patients to the rheumatology service.

In the case of control participants for the microbiota analysis, patients can opt in or out of having a family member as a control participant. If the patient agrees, he/she will be asked to pass the Patient Information Leaflet (PIL – control version) to their relative who will be invited to contact the study team if they are interested in participation. Family members can be first degree or second degree relatives of the same sex. In the event that no family member is suitable or willing to be involved then an age-similar, sex-matched control may be recruited from the staff of the University of Edinburgh, the Western General Hospital or SHARE.

Study participants in both the GoutSMART, as well as the microbiome part of the project who fail screening will be considered for re-screening within one month of initial screening. Subjects of the microbiome control group will be considered for re-screening up to 3 months from initial screening.

All patients of the GoutSMART active and control arm completing the study at week 52 will be invited to participate in the extension study.

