6 STUDY PROCEDURES AND ASSESSMENTS

6.1 STUDY PROCEDURES

6.1.1 Baseline visit

Written and informed consent will be obtained. A history will be taken, basic anthropometric measurements taken (blood pressure, weight, waist circumference) and physical examination be performed. Full medication history will be obtained from participants. Blood samples will be taken for measurement of urate, full blood count, renal and liver function and oxypurinol levels. A finger prick testing for urate levels will be carried out. Participants will be asked to collect urine over a period of 24hrs to hand into the lab as soon as feasible after the baseline visit. A blood sample for creatinine and urate will be taken at that point for paired analysis with urine. Eligible subjects will be randomised at a 1:2 ratio to usual care or supported self-management using a web-based randomisation tool.

For the purposes of the microbiome analysis, patients will provide a once off stool and urine sample at baseline in addition to filling an online food frequency questionnaire. For control subjects for the microbiome analysis, participants will attend on one occasion to provide written informed consent, medical history review, FFQ, blood samples for urate, renal and liver function and oxypurinol levels. In addition they will provide an early morning urine sample and a fresh faecal sample. They will also be asked to collect urine over the 24hour period and a paired serum renal function and urate blood sample will be taken when handing the collection in. No further follow-up visits are planned.

No payment shall be made for participation in the study but compensation for costs of travel to the Western General Hospital shall be offered to control participants up to a value of £30

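### Gut-related exclusions in Section 4.3 apply to the microbiome controls but not to the gout participants, so the gout-versus-control comparison is open to confounding

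*Combined protocol and SAP*

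**What the plan says.** Section 4.3 gives general exclusions for the study, then a second list for the microbiota part, introduced by "subjects are excluded from the control group if any of the previous or following are present". Besides a history of gout and current urate lowering therapy, that list contains four gut criteria. The one on antibiotics reads "Have had oral antibiotics in the previous 3 months". The other three cover past bowel inflammation or bowel cancer, surgical removal of the colon, and a gut infection within six weeks.

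Gout participants enter under Section 4.2, which requires a "Physician recommendation that initiation or escalation of urate lowering therapy (Allopurinol or Febuxostat) is required". Someone already on treatment can therefore join. Section 6.1.1 states that "patients will provide a once off stool and urine sample at baseline".

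Controls are relatives or volunteers. For relatives, Section 5.1 says: "Family members can be first degree or second degree relatives of the same sex". Only the non-family controls must also be of similar age. Section 5.1 allows re-screening within one month for study participants, including those in the microbiome part, and up to three months for microbiome controls.

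Section 8.2 contains no microbiome or metabolite analysis.

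**The concern.** By listing the four gut criteria, the plan treats them as relevant to stool and urine measurements, yet it filters only one side of the comparison. Section 1.1 sets out to test and develop the idea that gut bacteria differ between people with gout and controls, and about 60 controls are recruited for this. If recent antibiotics or bowel disease occur among the gout participants and have been removed from the controls, a difference could reflect those factors and not gout.

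The drug raises a related but distinct problem. Section 6.3 measures metabolites of purine and uric acid metabolism, and the treatments named in Section 4.2 are given to lower urate. If treated gout participants are compared with untreated controls, the difference combines disease and drug. Age adds to this, because a same-sex parent, child or grandchild qualifies as a control.

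Each participant gives one baseline sample, so the design offers no later stool sample with which to repair the comparison.

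**Working it through.** **Reading the text.** I looked for any restriction, matching or adjustment that would put the two groups on the same footing.

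| Factor | Controls | Gout participants |
|---|---|---|
| Oral antibiotics, 3 months | excluded (4.3) | no criterion |
| Inflammatory bowel disease or colorectal cancer | excluded (4.3) | no criterion |
| Total colectomy | excluded (4.3) | no criterion |
| Gut infection, 6 weeks | excluded (4.3) | no criterion |
| Urate lowering therapy | excluded (4.3) | allowed unless already at maximum (4.2, 4.3) |
| Age | similar for volunteers, unmatched for relatives (3.1, 5.1) | not applicable |

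Nothing in Section 8.2 adjusts for any of these.

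**Plan's own figure.** There is none to reproduce. The power figures in Section 8.1 concern the randomised comparison and the extension.

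**Illustrative bias from the gut factors.** The group sizes, 60 and 60, come from the synopsis and Section 4.1. I assumed the exposed fraction p among gout participants (10-20%), the effect e of exposure (0.5-1 SD), zero exposure in controls, no true gout effect, and one two-sided 5% t-test.

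- Spurious difference: d = p × e.
- Noncentrality: d / √(1/60 + 1/60) = d × √30, with 118 degrees of freedom.

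| p | e (SD) | d (SD) | d × √30 | Chance of a false positive |
|---|---|---|---|---|
| 10% | 0.5 | 0.05 | 0.27 | 5.8% |
| 10% | 1.0 | 0.10 | 0.55 | 8.4% |
| 20% | 0.5 | 0.10 | 0.55 | 8.4% |
| 20% | 1.0 | 0.20 | 1.10 | 19.2% |

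A normal-approximation version that allows for the extra variance among the exposed gives nearly the same results (18.4% in the last row).

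**The same sum for the drug.** If 30-70% of gout participants were treated at sampling and treatment shifted a metabolite by 0.5 SD, d would be 0.15-0.35 SD and the chance of a significant difference without any disease effect 13-48%. Both inputs are again assumed.

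**Cost in precision.** The difference detectable with 80% power is (1.960 + 0.842) × √(1/n + 1/60), where n is the number of gout participants analysed and 60 is the number of controls.

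| Gout participants analysed | Detectable difference (SD) |
|---|---|
| 60 (all) | 2.802 × 0.183 = 0.51 |
| 54 (10% fail a gut criterion) | 2.802 × 0.188 = 0.53 |
| 42 (untreated, if 30% are treated) | 2.802 × 0.201 = 0.56 |
| 18 (untreated, if 70% are treated) | 2.802 × 0.269 = 0.75 |

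The last two rows start from all 60. Applying the gut criteria as well would lower n further.

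**Adjusting for the drug gains little over restriction.** No control takes urate lowering therapy. In an additive model with one term for gout and one for therapy, the gout coefficient is therefore, apart from the age term, the untreated-gout-versus-control difference.

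**The case against.** The strongest reply is that this is an exploratory part of a feasibility study, with no power claim of its own, and that the objective in Section 2.1.2 is a correlation between faecal uric acid load and microbiome characteristics, not a group contrast. That stands. The correlation is affected only if gout participants and controls are pooled, or if a factor such as the drug or an antibiotic alters both measures. A reader might infer that the stated secondary objective will get a wrong answer; its wording does not support that. The group question comes from Section 1.1 and from the recruitment of controls.

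A second reply is that excluding treated people from the controls is no fault. This also stands. Controls must have no history of gout, so the exclusion is reasonable. What is missing is any plan to separate treated from untreated gout participants.

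Third, the text may imply some screening of gout participants. Section 3.1 says that eligible participants join the gut part, and Section 5.1 speaks of microbiome participants who fail screening. Neither names a gut criterion, so neither closes the gap. Excluding azathioprine and mercaptopurine users (Section 4.3) and asking for formed stool (Section 6.2.7) may remove some bowel disease or acute illness, but they do not address antibiotics.

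Finally, the percentages belong to a single unadjusted t-test that the plan does not specify, whereas the data are metagenomic and metabolomic. That is fair: they show scale only.

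**Conclusion.** The one-sided use of the four gut criteria is plain from the text, and nothing elsewhere in the plan offsets it. It leaves the gout-versus-control comparison open to avoidable confounding. It would go too far to say that the comparison is confounded, because the documents do not say how common these exposures are among gout participants. Under the assumed 10-20% exposure and 0.5-1 SD effect, the false-positive rate is about 6-19%. At the low end that is barely above 5%, and rare factors such as colectomy would contribute little.

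The mixing of disease and drug effects is a separate gap in the analysis plan. The 13-48% range might be read as an estimate of error in this study. It is not, since both the treated fraction and the drug effect are assumed.

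The randomised comparison of urate at 24 weeks is untouched. This is a cheap improvement to a secondary part of the study.

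**What to change.** **Section 4.3.** State that the antibiotic, bowel disease or colorectal cancer, colectomy and gut-infection criteria also apply to gout participants, for entry to the microbiome sub-study only. Those who fail stay in the randomised trial.

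**Section 5.1.** Reconcile the re-screening windows with the 3-month antibiotic criterion. A gout participant who has just finished antibiotics cannot meet it within the one-month window, and a control in the same position meets it only at the very end of the three-month window. The text should also say how a postponed sample fits with the baseline sampling in Section 6.1.1, since treatment may have started or changed by then.

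**Section 8.2.** Add a gout-versus-control analysis of the microbiome and metabolite measures, adjusted for age. Report it for all gout participants and for those not on urate lowering therapy at sampling. The medication history taken at baseline (Section 6.1.1) identifies the second group. Keep the exclusion of treated controls.

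**Cost.** The text changes are a sentence in Section 4.3, a clarification in Section 5.1 and a short new analysis paragraph in Section 8.2, which has none to amend. About 6 of 60 gout participants leave the sub-study for each 10% excluded; at 10% the detectable difference moves from 0.51 to 0.53 SD. The untreated contrast is less precise, at about 0.56-0.75 SD if 30-70% are treated. If samples have already been collected, the Section 8.2 change can still be made.

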4.4 CO-ENROLMENT

Co-enrolment will not be allowed in any circumstances.

5 PARTICIPANT SELECTION AND ENROLMENT

5.1 IDENTIFYING PARTICIPANTS

Participants will be identified by the principal investigator or the sub-investigator following assessment by the NHS Lothian Rheumatology service. It is anticipated that most participants will be identified following routine and acute-care referrals to NHS Lothian Rheumatology services by the participants' general practitioner or secondary care physicians, however any appropriate referral will be considered including referrals from out with NHS Lothian. Additional participants will be sought through SHARE - The Scottish Health Research Register which is a register of adults and children aged 11 and over who are willing to be invited to take part in medical research.

Posters raising awareness of the study will be placed in the rheumatology outpatient department, and in Acute receiving units at Western General Hospital and Royal Infirmary of Edinburgh. An email will be sent to General Practitioners in NHS Lothian inviting referral of suitable patients to the rheumatology service.

In the case of control participants for the microbiota analysis, patients can opt in or out of having a family member as a control participant. If the patient agrees, he/she will be asked to pass the Patient Information Leaflet (PIL – control version) to their relative who will be invited to contact the study team if they are interested in participation. Family members can be first degree or second degree relatives of the same sex. In the event that no family member is suitable or willing to be involved then an age-similar, sex-matched control may be recruited from the staff of the University of Edinburgh, the Western General Hospital or SHARE.

Study participants in both the GoutSMART, as well as the microbiome part of the project who fail screening will be considered for re-screening within one month of initial screening. Subjects of the microbiome control group will be considered for re-screening up to 3 months from initial screening.

All patients of the GoutSMART active and control arm completing the study at week 52 will be invited to participate in the extension study.

5.2 CONSENTING PARTICIPANTS

Written and informed consent will be obtained by the principal investigator or the sub-investigator prior to any study-related procedures being undertaken. Verbal and written participant information will be presented to the participant detailing the nature of the study, the

implications and constraints of the protocol; the known side effects and any risks involved in taking part. It will be clearly stated that the participant is free to withdraw from the study at any time for any reason and without prejudice to future care, and with no obligation to give the reason for withdrawal. The participant will be allowed as much time as wished to consider the information, and the opportunity to question the Investigator, the GP or other independent parties to decide whether they will participate in the study. Written Informed consent will then be obtained by means of the participant dated signature and dated signature of the person who presented and obtained the informed consent. A copy of the signed Informed Consent will be given to the participants. The original signed form will be retained at the study site.

Patients invited to participate in the extension phase of the study will be provided with written information about the extension via email or in the post with at least 48 hrs time to read the information prior to there week 52 review. Consent will be obtained either during the face to face visit. To minimise COVID-19 exposure, consent may be obtained following a telephone review. The participant may sign the PIL at home and email or post this back to the researcher.

5.3 Withdrawal of Study Participants

Participants are free to withdraw from the study at any point or a participant can be withdrawn by the Investigator. Withdrawal by the investigator will be considered when participants are non-compliant with study procedures. At least two attempts will be made to contact the participant to ascertain whether the participant wishes to continue the study.

If withdrawal occurs, the primary reason for withdrawal will be documented in the participant's case report form, if possible. The participant will have the option of withdrawal from

- (i) all aspects of the trial but continued use of data collected up to that point
- (ii) all aspects of the trial with removal of all previously collected data.
- (iii) all aspects of the trial with removal of previously collected and stored participant samples.

6 STUDY PROCEDURES AND ASSESSMENTS

6.1 STUDY PROCEDURES

6.1.1 Baseline visit

Written and informed consent will be obtained. A history will be taken, basic anthropometric measurements taken (blood pressure, weight, waist circumference) and physical examination be performed. Full medication history will be obtained from participants. Blood samples will be taken for measurement of urate, full blood count, renal and liver function and oxypurinol levels. A finger prick testing for urate levels will be carried out. Participants will be asked to collect urine over a period of 24hrs to hand into the lab as soon as feasible after the baseline visit. A blood sample for creatinine and urate will be taken at that point for paired analysis with urine. Eligible subjects will be randomised at a 1:2 ratio to usual care or supported self-management using a web-based randomisation tool.

For the purposes of the microbiome analysis, patients will provide a once off stool and urine sample at baseline in addition to filling an online food frequency questionnaire. For control subjects for the microbiome analysis, participants will attend on one occasion to provide written informed consent, medical history review, FFQ, blood samples for urate, renal and liver function and oxypurinol levels. In addition they will provide an early morning urine sample and a fresh faecal sample. They will also be asked to collect urine over the 24hour period and a paired serum renal function and urate blood sample will be taken when handing the collection in. No further follow-up visits are planned.

No payment shall be made for participation in the study but compensation for costs of travel to the Western General Hospital shall be offered to control participants up to a value of £30

6.1.2 Intervention procedures

Based on the baseline renal function and serum urate levels, and in line with local protocols, an individual treatment plan will be drawn up for all participants in both groups. This includes a management plan for a potential episode of gout-flare and offering of flare prophylaxis. The treatment plan will be sent to the general practitioner and the patient copied in. All participants will be examined at baseline and the number and size of tophi (if present) will be recorded.

All participants will have the GoutSMART application installed on their phones, and be taught how to use the application to allow direct communication between the research staff and the participant. All participants will be given access to online resources providing background information on the causes of gout, the likely progression of symptoms, strategies for dealing with acute attacks of gout and the importance of controlling serum urate levels. All participants will be prompted once per month to enter information about their disease severity including the number of days of flare per month, health related quality of life during and after flares, number of days lost at work and the number of health care appointments attended.

Participants in the intervention group will receive their treatment plan in the same fashion and will be provided with the BeneCheck hand-held device, taught to perform the serum urate finger prick self-test and shown how to enter this information into the application. Participants will be sent automatic reminders two weeks after any increased dose of urate lowering therapy (including that of the plan set during baseline clinic consultation) to test their own urate levels and submit updated readings. If urate levels remain above target, written advice to increase the dose of urate lowering will be sent to the patient and supervising physician advising up-titration of therapy, with this confirmed also by text message. If up-titration is recommended, a reminder to test again will be sent after a further two weeks. Conversely, for participants achieving target levels, acknowledgement will be sent and a request to resubmit readings will be sent on a monthly basis until three consecutive target readings have been obtained. Six months are allowed to ensure that all participants have the opportunity to escalate to maximum therapy and potentially switch to alternative urate lowering therapy if required.

6.1.3 End-of study visit week 24

Participants will be invited to the RDU clinic, or alternatively if hospital attendance is not appropriate due to recommendations to self-isolate or maintain social distancing due to the coronavirus pandemic then this assessment will be made by telephone. The patient diaries generated by the GoutSMART application will be reviewed and any adverse advents recorded. Participants will complete a questionnaire on their experience with standard care or the testing device and the smart phone application. All participants will be asked to record the number of doses of medication missed in the preceding 2 weeks. A physical examination will be performed to assess the size and number of tophi, or submitted images will be reviewed. Finger prick and/or serum urate will be measured along with blood tests of full blood count, renal and liver function tests and oxypurinol levels. A letter will be written to the GP of all participants summarising the disease course and management throughout the past 24 weeks and proposing further management advice. All participants will retain access to the smart phone application and be asked to enter information about the disease course on a monthly basis until week 52.

